6.2.1 Additional analyses

For subjects undergoing surgery (both major and minor), the following information will be listed:

- Blood loss
- Need for additional hemostatic medication, including blood products
- Units of blood transfused
- Hemostatic-related surgical complications
- Assessment of hemostasis as excellent, good, moderate or poor
- Study drug usage

Factor VIII concentration values and recovery values will be listed where available. As only few values are expected, no tabulation will be done.

Health care resource utilization will be tabulated. This includes additional visits to hematologists, family physician, nurse or other health care provider, additional tests, like blood tests but also radiological tests, hospital visits and nights in hospital.

6.2.2 Subgroup analysis

Subgroups of analysis are already described in 4.1:

- ➤ type of subjects: PUPs; MTPs; total
- inhibitor status: Subjects without inhibitor; Subjects with low titer inhibitor; Subjects without inhibitor or with low titer inhibitor; Subjects with high titer inhibitor
- > inhibitor status of PUPs: The same as above restricted to PUPs

These different periods for analysis are planned:

Period	Definition	To be used
Total part B period	MAINSDTM to MAINEDTM	always
		for response to
On-demand period	if OD_STDTM >. : OD_STDTM (is equal to	treatment of
	MAINSDTM) to OD_EDTM	bleeds

Statistical Analysis Plan PH-41074

Protocol No.: BAY	81-8973 / 13400
-------------------	-----------------

Page: 15 of 19:

Period	Definition	To be used
Prophy period (without once per week treatment)	if an infusion with EXSCATN = 8 exists and last infusion with EXSCATN = 8 < MAINEDTM: last infusion with EXSCATN = 8 to MAINEDTM. If last infusion with EXSCATN = 8 is at MAINEDTM no such period exists. If no infusion with EXSCATN = 8 exists: PX SDTM to PX ENDTM.	later for publications
Prophy period (including once per week treatment)	if SDTM > .: PX SDTM to PX ENDTM	always
Total treatment period (starting after 1st treatment)	TRTSDT to MAINEDTM	always
Period of once per week treatment only	if an infusion with EXSCATN = 8 exists: if OD_STDTM ne . then PX_SDTM to last infusion with EXSCATN = 8 else TRTSDT to last infusion with EXSCATN = 8	later for publications
Period of high inhibitor of high titer inhibitor subjects	if HINHSDTM < HINHEDTM: HINHSDTM to HINHEDTM	For extension only
Period of total inhibitor of high titer inhibitor subjects	if HINHSDTM > .: INHSDTM to INHEDTM	For extension only
Period of total inhibitor of low titer inhibitor subjects	if HINHSDTM = . and INHSDTM < INHEDTM: INHSDTM to INHEDTM	ABR & response to treatment

Further specification of the different periods are as following:

- The **total part B period** starts with the baseline visit and ends with the final visit. In case the study drug were already administered between the screening visit and the baseline visit, the period starts with the date of injection.
- The **on-demand period** starts with the first injection in an on-demand schedule and ends with the start of the prophylaxis period or final visit, whatever comes first.
- The **prophylaxis** period starts with the first and ends with the last injection of prophya ctic study drug.
- The **total treatment period** starts with the first injection of study drug and end with th e final visit.
- The period of low titer inhibitor starts with the day when low titer inhibitor was detected and ends with either the final visit or the day when no inhibitor was detected, whatever comes first.

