6.4 Dosage and administration

The dose selections for this study are based on the recommended dosage for Kogenate® FS/Bayer.⁶ The study medication, BAY 81-8973, has been shown to have similar biological activity to Kogenate® FS/Bayer, which is currently approved in more than 50 countries for the treatment of hemophilia A.

In Part A of this study (as of Amd 1), subjects will receive prophylaxis treatment with BAY 81-8973 at least 2 times weekly with a dose of 25-50 IU/kg at the choice of the investigator and according to local standards and previous treatment. The dose *should be rounded to the appropriate vial size. In Part B, prophylaxis may be started with a low dose, once a week treatment schedule. The recommended dose is 15-50 IU/kg, (minimum 250 IU) (as of Amd 6). For all subjects, the (as of Amd 1)* frequency as well as the dose may be adapted to the individual needs up to daily if needed to accommodate for the subject's activities *or sports participation. (as of Amd 1)*

Any bleeding *events* occurring in subjects receiving prophylactic care will be treated according to the *local* standard of care and severity of the bleed. *(as of Amd 1)*

Subjects will be injected by parents/caregivers at home, *at a* facility near *the* subject's home, *homecare nurse (as of Amd 1)*, or by the investigator/delegate during the study visits. Children may also *self-infuse, if under the supervision of a responsible adult to ensure adherence to the prescribed treatment regimen. (as of Amd 1)*

For the optional PK study, each subject will receive *an exact* dose of 50 IU/kg of BAY 81-8973. The dose will be prepared by a pharmacist or nurse at the study *site*. This dose *is* expected to increase the plasma level of FVIII to approximately 80-100% FVIII activity. *(as of Amd 1)*

During surgery (both major and minor) dosing with BAY 81-8973 will follow the same standard practice as followed for Kogenate® FS/Bayer (Appendix 14.1). The guidelines are designed to maintain adequate hemostatic FVIII levels and provide instructions based upon the type of surgical procedure to be undertaken. *(some text deleted as of Amd 1)*

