4.5.2 Annualized bleed rate

The definition of annualized bleed rate is generally defined as

```
(#of bleeds in period) * 365.25/(last datetime of period- first datetime in period)
```

```
60 \cdot 60 \cdot 24
```

The different periods used for analysis are described in section 6.2.1.

4.5.3 24 hours rule

Count no more than 1 bleed in a calendar day. If there is more than 1 bleed in a calendar day, to determine the bleed that gets counted, give priority to treated bleeds, spontaneous or trauma bleeds, then joint bleeds. Otherwise, count the first bleed in the day. Severity and treatment response will come from this selected bleed. Bleed site will be aggregated over all bleeds from that day. Regardless of which bleed is selected, the time of the first bleed in the day will be used. All other infusions in the day for treating bleeds will be considered follow-up infusions.

4.5.4 72 hours rule

Do not count a spontaneous joint/muscle bleed if it occurs within 72 hours of a bleed (or infusion for that bleed) at the same site. For a bleed to be affected by this rule, all sites listed on the bleed must also be specified in the previous bleed. If the current and previous bleeds are both skin/mucosa bleeds, this rule does not apply. Such infusions for bleeds will be considered to be follow-up infusions.

Joint bleeds can occur in more than 1 joint site. For each joint bleed, count all sites (combining left and right). For the table showing the Joint Site frequency, sum counts over all sites.

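### In the Part B SAP the more-than-once-weekly prophylaxis period ends at the final visit for children with any once-weekly infusion but at the end of prophylaxis for the rest, and the cut at the last weekly infusion fails if a child returns to weekly dosing

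*SAP*

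**What the plan says.** The period table in Part B SAP v2.0, section 6.2.2, has two rows that separate once-weekly from more frequent prophylaxis.

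- **More-than-once-weekly prophylaxis.** If an EXSCATN = 8 infusion exists and the last one precedes MAINEDTM, the period is "last infusion with EXSCATN = 8 to MAINEDTM. If last infusion with EXSCATN = 8 is at MAINEDTM no such period exists". Otherwise: "If no infusion with EXSCATN = 8 exists: PX SDTM to PX ENDTM".
- **Once weekly only.** "if OD_STDTM ne . then PX_SDTM to last infusion with EXSCATN = 8 else TRTSDT to last infusion with EXSCATN = 8".

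MAINEDTM closes the total Part B period, which "starts with the baseline visit and ends with the final visit". The text below the table says that the prophylaxis "period starts with the first and ends with the last injection of" prophylactic study drug. The broader prophylaxis row, which includes weekly treatment, runs from the start to the end of prophylaxis (PX ENDTM).

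Both regimen-specific rows are marked "later for publications". Annualised rates (SAP 4.5.2) are bleeds in the period times 365.25, divided by the length of the period in days.

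On changes of regimen, Protocol 6.4 says that the "frequency as well as the dose may be adapted to the individual needs", up to daily if needed. The Part B recommendations in Protocol 6.1.1 name only increases.

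**The concern.** One row has two end points, and the choice between them depends only on whether a child ever had a weekly infusion. The final-visit rule lets the sub-period run past the end of the prophylaxis period that should contain it. Protocol 7.1.2 expects most Part B subjects to begin prophylaxis once weekly, so if EXSCATN = 8 marks those infusions, the final-visit branch is probably the usual one. Children who stop prophylaxis because of an inhibitor are foreseen in SAP 4.2, and efficacy is displayed by inhibitor status, so any off-prophylaxis time and bleeds would collect in particular columns.

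The second weakness is the cut itself. A single late EXSCATN = 8 infusion moves all earlier prophylaxis, at whatever frequency, into the once-weekly period.

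At stake is any published description of bleeding on weekly against more frequent prophylaxis. These are the only two prespecified periods that separate them.

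**Working it through.** The plan gives no figure to reproduce, so I applied its rules to constructed schedules. All schedules and gaps are assumptions, not trial data.

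**Inputs.** Period rules: SAP 6.2.2. Rate formula: SAP 4.5.2. Gap g from the last infusion to the final visit: 0 to 14 days for completers if the 50th exposure day is the last prophylactic infusion, since Protocol Table 7-2b requires the visit within 2 weeks of 50 ED. The documents give no maximum gap for early stoppers; 28 and 56 days are used for illustration.

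**Method.** Infusions start on day 0, every 7 days (1x) or every 3.5 days (2x). Time on a regimen is the sum of the intervals that follow each infusion, up to the last prophylactic infusion. Example, schedule A: last weekly infusion on day 11 × 7 = 77; last infusion on day 84 + 37 × 3.5 = 213.5. The rule as written gives 77 days once weekly and 213.5 + g − 77 = 136.5 + g days more often.

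| Schedule | Time on regimen, days (1x / more) | Rule as written, days (1x / more) |
|---|---|---|
| A: 12 wk 1x, 19 wk 2x | 84 / 129.5 | 77 / 136.5 + g |
| B: 12 wk 1x, 12 wk 2x, 4 wk 1x, 5 wk 2x | 112 / 115.5 | 189 / 38.5 + g |
| C: 12 wk 1x, 17 wk 2x, 4 wk 1x | 105 / 119 | 224 / g |
| D: 50 wk 1x | 343 / 0 | 343 / g |
| E: 12 wk 1x, 4 wk 2x, then stopped | 84 / 24.5 | 77 / 31.5 + g |
| F: 25 wk 2x | 0 / 171.5 | none / 171.5 |

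**End rule.**
- D with g = 7 or 14: a period labelled as more frequent prophylaxis exists although none was given. One bleed in it gives 365.25/7 = 52.2 or 365.25/14 = 26.1 per year.
- E with g = 28: 28/59.5 = 47% of the period has no prophylaxis. With g = 56: 56/87.5 = 64%.
- F has no tail whatever the gap, because the PX ENDTM branch applies. E and F show one period under two end rules.

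**Cut at the last weekly infusion.**
- A, a one-way step-up: no twice-weekly time falls in the once-weekly period. The final weekly interval (84 − 77 = 7 days) moves the other way.
- B: 84 of 189 once-weekly days (44%) were twice weekly.
- C: 119 of 224 (53%) were twice weekly.

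**With regimen-based segments ending at PX ENDTM**, the figures become those in the middle column, with no tail.

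**The case against.** The strongest reply is that little of this will matter in practice.

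- **Completers.** Study drug is infused at the final visit (Protocol 7.1.2.8), and recovery is measured with planned prophylaxis infusions (Protocol 7.3.2.1). If that infusion is coded as prophylaxis, the last prophylactic infusion and the final visit nearly coincide. This stands: the tail may be close to zero, and part of any tail is an ordinary dosing interval.
- **Return to weekly dosing.** No passage describes it. Protocol 6.1.1 names only increases, Protocol 6.4 gives upward examples, and the venous-access provision concerns missed infusions rather than a new regimen. This stands as to likelihood. It is still not excluded: Protocol 6.4 and the interim visit in 7.1.2.7 allow frequency to be adjusted without naming a direction.
- **Withdrawn children.** SAP 4.2 ends their annualised count at the last procedure in a visit or the last diary infusion. That does not repair the rule, because a visit procedure can come after prophylaxis has stopped. Display by inhibitor status separates many of these children but leaves the off-prophylaxis time in their columns.
- **Unseen specification.** EXSCATN = 8 is not defined in the SAP, and the separate dataset specification, which the SAP calls an integral part, might handle these cases. That limits certainty about the code, not about the two stated end points.

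A reader might infer that both periods end at the final visit, or that every step-up is mislabelled as once weekly. Neither follows. The once-weekly period ends at the last EXSCATN = 8 infusion, and schedule A shows that a single step-up puts no more-frequent time there.

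**Conclusion.** The end rule is wrong as written. It gives one period two end points, and one of them contradicts the SAP's own definition of prophylaxis. The error needs no unusual dosing pattern: it arises whenever a child with an EXSCATN = 8 infusion has a final visit after the last prophylactic infusion. Its size is at most about 2 weeks for completers (if the 50th exposure day is the last prophylactic infusion) and possibly longer after an early stop. The direction of bias in the annualised rate is not known, since both days and bleeds enter.

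The mislabelling of more frequent prophylaxis is conditional on a step-up followed by a return to weekly dosing. How often that happens cannot be judged from the documents.

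It would also be tempting to infer that the main Part B bleeding results are affected. They are not: the primary variable and the periods to be used always do not rely on the EXSCATN = 8 cut, and the prophylaxis period among them already ends at PX ENDTM. Part B efficacy is exploratory, without formal tests. The conclusion rests on reading EXSCATN = 8 as a once-weekly infusion, and the percentages illustrate assumed schedules.

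**What to change.** In Part B SAP section 6.2.2:

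1. End the more-than-once-weekly period at PX ENDTM for all children.
2. Create it only where more-than-once-weekly prophylaxis was given.
3. Assign time and bleeds to the regimen in force at each infusion, allow several segments per child, and sum them within each regimen.
4. State what EXSCATN = 8 means, and which codes or infusion dates identify the other regimens.

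The cost is a change of wording and slightly more programming on infusion records already collected. No new data are needed, and no primary or always-used analysis changes.

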- ***Treatment can be initiated with an on-demand regimen. Prophylaxis should begin after a minimal number of on-demand FVIII exposures with BAY 81-8973 (no more than 2-3 bleeding events) or when the child is large enough to tolerate weekly infusion. (as of Amd 1 and 6)***
- ***Alternatively, prophylaxis can be started directly with a once-a-week schedule low dose of 250 IU (15-25 IU/kg); the starting dose may be tailored to the subject's weight or demonstrated bleeding tendency. (as of Amd 1 and 6)***
- ***Increase frequency of infusion or dose as needed for breakthrough bleeding, increased physical activity, or weight gain. (as of Amd 1)***
- ***Avoid starting prophylaxis during febrile illness or other identified inflammatory events. (as of Amd 1)***
- ***Avoid surgery or need for high dose intensive treatment lasting more than 4 days during the first 20 ED. (as of Amd 1)***
- ***Do not give FVIII as prophylaxis for vaccinations. (as of Amd 1)***

After treatment with BAY 81-8973 begins (as of Amd 1), inhibitor testing every 3-5 ED is required (as of Amd 1) until 20 ED are accumulated or in case of non-response to treatment (Section 14.5) (as of Amd 1)

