7.3.2.2 Treatment logs / bleeding verification

Treatment (as of Amd 1) logs are commonly used for hemophilia subjects for documentation of their home treatment. Home treatment and bleeding frequency are key variables evaluated in this study. Study specific logs will be provided in national language. The preferred system for this study will be EPD devices since they are interactive, allow for real time data transmission, record-stamp date and time of fulfillment and facilitate the clarification of data with the site and also the data cleaning process.

Subjects/parents/caregivers will be provided with EPDs for the whole study. At Screening and Baseline visits, subjects and parents/caregivers will be trained in the use of the device. These logs will be used to collect the *treatment (as of Amd 1)* data and bleeding episodes by the parents/caregivers or subjects, and interact on a *regularly scheduled (as of Amd 1)* basis with the investigator or delegate to verify and complete the *data on (as of Amd 1)* the EPD. Thus, the EPD will be considered the source for these data.

For each *use* of study medication including the *infusions* administered during a planned visit for evaluation of recovery, information must be recorded on the *Treatment (as of Amd 1)*

Logs as follows:

1. Date and time
2. Lot numbers / number of vials administered

3. Reason for *treatment (as of Amd 1)* (prophylaxis, spontaneous bleed first treatment, trauma bleed first treatment, follow-up treatment, surgery, other). ***(If an infusion is given in response to a fall or identified trauma, such as may occur when a child has an uncomplicated blow to the head and there is no clinical sign or evidence of bleeding, the event should be recorded as prophylaxis.) (as of Amd 1)***

If treatment is for a bleeding episode: site of bleeding, severity (severe, moderate, mild), and response to treatment (excellent, good, moderate, *poor, too early to tell*) ***are to be recorded. If 'too early to tell' is entered, the subject will be queried for a response the next time they use the device. For guidance to the subject or their caregivers, the following definitions for response to treatment are suggested. Individual subject responses may vary (as of Amd 1):***

- ***Excellent: Abrupt pain relief and /or improvement in signs of bleeding with no additional infusion administered (as of Amd 1)***

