indicator variable: in reason for infusion was prophylaxis, was there a bleed within 48 hours (no/yes)

reason for infusion (prophylaxis (including additional prophylaxis), spontaneous-1st infusion, trauma-1st infusion, surgery, follow-up, other)

dose (IU)

most recent body weight

dose (IU/kg) [use most recent body weight]

time from last infusion to this infusion (days)

time of day [morning, (06:00 - 13:59), afternoon (14:00 - 21:59), night (22:00 - 5:59)] time from last prophylaxis infusion to this infusion (days)

An example for infusion/bleed/subject data is shown below. The subject has 182 days in study with 52 exposure days and total bleeds equal 2:

Infusions data set (ADXB)	Bleeds data set (ADXC)	Subject data set (ADXA)
Infusion #/reason	# of infusions per bleed/type	# of bleeds/

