5.1 Assignment of analysis sets

Final decisions regarding the assignment of subjects to analysis sets will be made during the review of study data and documented in the final list of important deviations, validity findings and assignment to analysis set(s) (see section 4.6).

The statistical analysis sets are defined as follows:

SAFety analysis set (SAF)

All subjects with at least one intake of study drug.

Subjects who were assigned to treatment but did not receive study medication will not be included in the SAF. As the number of these excluded subjects is anticipated to be negligible, if at all any exist in this design, an "all assigned treatment analysis set" will not be generated.

(modified) Intent To Treat Set (ITT)

All subjects of the SAF, who have infusion/bleeding data.

Per Protocol Set (PPS)

All ITT subjects who completed Part A and Part B of the study with no major protocol deviations.

Major protocol violations would be for example:

- Severe hemophilia A not confirmed
- Evidence of inhibitor antibody present at the time of screening.
- MTP has previously received more than 3 exposure days with any FVIII product, PUP has received any amount of FVIII
- In the prophylactic period here was/were at least
 - \circ one instance of >30 days between infusions
 - \circ two instances of >21 days between infusions
 - \circ three instances of >14 days between infusions

PharmacoKinetic Analysis Set (PK)

Statistical Analysis Plan PH-41074 Protocol No.: BAY 81-8973 / 13400

Page: 12 of 19:

Not applicable to this interim analysis, as it is not expected to get enough subjects for a reasonable analysis from part B. There will be an analysis of the pharmacokinetic data for the final CSR.

Listing Only Set (LOS)

Subjects who do not belong to SAF will not be included into statistical considerations. These subjects are classified as 'listing only set' (LOS). Number of screening failures and dropouts will be tabulated.

6. Statistical Methodology

The efficacy analyses will be based on the ITT and sensitivity analyses will be based on the PPS as appropriate.

The primary analysis population for the safety analysis will be the SAF.

6.1 **Population characteristics**

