6.2 Efficacy

All subjects receiving study drug who have infusion/bleeding data from the EPD will be included in the efficacy analysis.

Primary Efficacy Analysis

The primary efficacy variable according to protocol will be the annualized number of total bleeds (sum of spontaneous bleeds, trauma bleeds, untreated bleeds, and 'other' bleeds) that occur within 48 hours after all prophylaxis infusions. 'Other' bleeds are infusions with reason given as 'other'.

For this primary efficacy variable, the number of data available and missing data, mean, standard deviation (SD), minimum (Min), quartiles, median, and maximum (Max) will be summarized and presented.

Additional Efficacy Analysis

Also summarized will be annualized number of joint bleeds, spontaneous bleeds, and trauma bleeds that occur within 48 hours after all prophylaxis infusions. Additional variables summarized will be annualized number of total bleeds, joint bleeds, spontaneous bleeds, and trauma bleeds as well as the annualized numbers.

Other variables summarized will be the number of treatments required to control all bleeds and the subject's assessment of the response to treatment of all bleeds (excellent, good, moderate, or poor), further on description of joint bleeds according to site as well as proportion of subjects with no bleed

FVIII usage/consumption will be described expressed as number of infusions, number of prophylaxis infusions, and number of infusions to treat breakthrough bleeds. Infusions will be summarized in IU, IU/kg, IU/kg/year, IU/kg/infusion, IU/year, and IU/infusion.

All efficacy variables will be summarized using the ITT analysis set. The summary of bleeds, the exposure to study drug and the treatment administration for bleeds will also be given in the ITT.

The number of infusions used to treat a bleed will be summarized. The number of infusions used to treat a bleed is defined as the first infusion to treat the bleed plus all follow-up infusions to treat the same bleed, if any. The proportion of bleeds controlled by ≤ 2 and ≥ 2 infusions will be presented.

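### In Part B, one post-fall dose logged as prophylaxis starts the prophylaxis period during an on-demand lead-in, which misplaces time and bleeds in the prophylaxis bleed rate

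*SAP*

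**What the plan says.** - **On-demand lead-in.** Protocol 6.1.1, on PUPs and MTPs: "Treatment can be initiated with an on-demand regimen". Regular prophylaxis is then recommended after no more than 2-3 bleeding events, or once the child is large enough for weekly infusion.
- **Logging rule.** Protocol 7.3.2.2 covers an infusion given after a fall or a knock. Where it was given "and there is no clinical sign or evidence of bleeding, the event should be recorded as prophylaxis". The list of reasons for treatment in that section has one prophylaxis entry and none for a precautionary dose.
- **Period boundaries.** Part B SAP 6.2.2: the prophylaxis "period starts with the first and ends with the last injection of" prophylactic study drug. The on-demand period "ends with the start of the prophylaxis period or final visit, whatever comes first". The period table marks the prophylaxis period (including once-weekly treatment) for use always, and the on-demand period for response to treatment of bleeds.
- **Use of the rate.** Section 2.1 of the SAP supplement of 28 January 2020 makes annualized total bleeds during prophylaxis a secondary endpoint, calculated by the formula in Part B SAP 4.5.2.
- **Per-protocol set.** Part B SAP 5.1 lists gap criteria, introduced by "In the prophylactic period here was/were at least": one gap above 30 days, two above 21 days, or three above 14 days between infusions.

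**The concern.** Each rule is reasonable alone; the problem is their combination. A toddler still treated on demand falls, receives one precautionary infusion and does not bleed. The diary entry reads prophylaxis. Under 6.2.2 that entry opens the prophylaxis period and closes the on-demand period, although no regular schedule has begun.

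What is at stake is the meaning of the rate during prophylaxis. It should describe children on the regimen. For an affected child it also contains part of the on-demand lead-in, and the bleeds in that part no longer count in the on-demand response-to-treatment summary. The long intervals typical of on-demand treatment also become gaps inside a nominal prophylaxis period.

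**Working it through.** The documents give no figure for this effect, so the check applies the SAP's own formula under the two possible period starts.

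**Formula** (Part B SAP 4.5.2): rate = bleeds in period × 365.25 / days in period.

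**Inputs**
- 2 bleeds in 182 days on the regimen. These are the figures in the worked example in Part A SAP 6.2.1, used here for illustration. Protocol 7.1.2.8 expects most Part B children to reach 50 exposure days 6 to 12 months after starting prophylaxis, so 182 days is the short end.
- Lead-in days between the post-fall dose and the first regimen dose: 30, 90 or 180 (assumed).
- Bleeds in that interval: 0 to 3 (assumed; 3 is the upper end of the 2-3 on-demand bleeds in protocol 6.1.1).

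**Period starting at the first regimen dose:** 2 × 365.25 / 182 = 4.01 per year.

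**Period starting at the post-fall dose:** (2 + bleeds moved) × 365.25 / (182 + days moved). For 90 days: 2 × 365.25 / 272 = 2.69 with no bleeds moved, and 5 × 365.25 / 272 = 6.71 with three.

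| Days moved | 0 bleeds | 1 bleed | 2 bleeds | 3 bleeds |
|---|---|---|---|---|
| 30 | 3.45 | 5.17 | 6.89 | 8.61 |
| 90 | 2.69 | 4.03 | 5.37 | 6.71 |
| 180 | 2.02 | 3.03 | 4.04 | 5.04 |

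With 2 bleeds in 365 days on the regimen, 2.00 per year becomes anything from 1.34 (180 days, no bleeds) to 4.62 (30 days, three bleeds).

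**Direction.** The rate rises when bleeding in the moved interval is above the regimen rate and falls when it is below. The break-even for 90 days is 2 / 182 × 90 = 0.99 bleeds, which is why one bleed moved leaves 4.01 almost unchanged at 4.03.

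**Effect on a group mean.** In the 90-day, three-bleed case one child shifts by 6.71 − 4.01 = 2.70 per year. That moves a mean by 2.70 / 50 = 0.05 over about 50 children, 2.70 / 25 = 0.11 over 25, and 2.70 / 5 = 0.54 in an assumed inhibitor stratum of 5.

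**Edge cases.** A child who never starts a regimen but has two post-fall doses 60 days apart, with 2 bleeds between them, gets a prophylaxis rate of 2 × 365.25 / 60 = 12.2 per year. With one such dose the period has zero length and the rate is undefined.

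**Per-protocol gaps.** Infusions given for bleeds also break gaps. To meet none of the three criteria, the longest interval must be at most 30 days, the second at most 21, and all others at most 14. Three infusions inside a 90-day interval make four gaps, which can then cover at most 30 + 21 + 14 + 14 = 79 days, so a criterion is met. Four infusions make five gaps, which can cover 93 days, so the criteria can be avoided if the infusions are well spaced.

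**The case against.** **The derivation is not visible.** The table in 6.2.2 uses coded start and end variables (PX_SDTM and PX_ENDTM) that the supplied text does not define, and dataset rules sit in a separate Analysis Datasets document. An infusion code that appears to mark once-weekly doses suggests that the programming may not rest on the raw diary reason. This stands as a limit on what can be known. It does not remove the point: the wording on period boundaries was added deliberately (document history, entry for 16 January 2020), and a derivation that departs from it would contradict the SAP. The Part A SAP offers no rescue, because its infusion dataset pools the category as "prophylaxis (including additional prophylaxis".

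**The effect is partly contained.** The total Part B period and the total treatment period are also always reported, and neither depends on this boundary. Sites check diary entries weekly, and the analysis is descriptive. All of this stands and limits the consequence. It does not correct the rate during prophylaxis.

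**Stronger readings that a reader might infer, which the documents do not support**
- *The prophylaxis rate is biased upward.* The table in the working shows both directions, and nothing in the documents fixes the lead-in bleed rate.
- *Affected children are removed from the per-protocol set.* Section 5.1 gives the gap criteria as examples and leaves assignment to the data review. The set serves only sensitivity analyses.
- *The primary variable is corrupted by the same rule.* It counts bleeds that "occur within 48 hours after all prophylaxis infusions", so a post-fall dose opens a window wherever the period starts. Whether it should is a separate definitional choice.
- *The lead-in is untreated time.* Children in it receive study drug for bleeds.
- *Logging as prophylaxis is mandatory.* The protocol says should.

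**Conclusion.** The point holds for Part B. Followed as written, the logging rule and the period definition place the boundary between on-demand and prophylaxis at an isolated precautionary dose. Time always moves across the boundary; bleeds move only if they fall after that dose and before the regimen starts. For one child the distortion can be large in either direction (4.01 per year becomes 2.02 to 8.61 over the assumed range). For the whole group it is small unless several children are affected or the stratum is small. The documents do not say how many children had an on-demand lead-in or a post-fall dose within it, so the overall size cannot be stated. The conclusion rests on the SAP wording being the operative definition. It is worth correcting because the rate is a named secondary endpoint and the correction is simple.

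**What to change.** In Part B SAP 6.2.2, define the start of the prophylaxis period (PX_SDTM) as the first infusion of the regular prophylaxis regimen, with the date taken from site records. State that an isolated precautionary dose logged as prophylaxis does not start that period, end the on-demand period, or start the per-protocol gap count. Report the as-logged definition as a sensitivity analysis.

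The treatment of post-fall doses in the 48-hour primary variable can stay as it is, with at most a further sensitivity analysis. While editing, correct the cross-reference in 4.5.2, which sends the reader to 6.2.1 for periods that are defined in 6.2.2.

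The cost is a derivation change and a data query for each child with an on-demand lead-in, because the diary's single prophylaxis entry cannot identify these doses. Part B SAP 4.3 already plans to compute age at start of prophylaxis, which suggests that a start date is held. The site must still confirm that it marks the regimen: the regimen instruction in protocol 7.1.2.2 is a Baseline item and does not date a later start, and the SAP expects few recovery measurements.
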